4. INVESTIGATIONAL PLAN

4.1. Discussion of Study Design

This is a Phase I, open-label, multi-center, non-randomized, 2-part study. Part 1 is a dose escalation phase to determine the MTD and/or RP2D for GSK2879552, alone or in combination with ATRA, based on the safety, tolerability, pharmacokinetic, and pharmacodynamic profiles observed after oral administration of GSK2879552. Eligible subjects with relapsed/refractory acute myeloid leukemia or elderly subjects who are ineligible for or refuse induction therapy will be enrolled. Any dose level(s) may be expanded up to 12 subjects in order to collect additional data on safety, tolerability, PK and PD.

[figure not shown]
Once MTD and/or RP2D is identified, an expansion cohort (Part 2) of up to 30 subjects each will be enrolled to further evaluate the efficacy and tolerability of GSK2879552, alone or in combination with ATRA, in subjects with relapsed/refractory AML.

The proposed treatment schedule of GSK2879552 is continuous daily dosing. The starting dose for GSK2879552 mono therapy arm will be 0.25 mg/day or the highest dose determined to be safe in the ongoing SCLC study, whichever is higher with a maximum of 1 mg/day (see Section 1.4.3.2 for details). The starting dose of GSK2879552 in combination with ATRA will be 1-2 dose levels below the highest dose determined to be safe in the GSK2879552 mono therapy arm in this study, i.e., 2 mg once daily. Alterations to the dose and schedule may be incorporated based on emerging PK, PD, and tolerability data.

Dose reduction and/or truncated dose scheduling may be considered for subjects with recurrent/ persistent toxicity or according to the institutional guideline. For example, once the disease control (CR, CRp, PR or a morphologic leukemia-free state) is attained, ATRA may be given in an intermittent schedule, e.g., 2 week on/2 weeks off.

Subjects may continue treatment in the study until disease progression, unacceptable toxicity, or withdrawal of consent. The duration of study will depend on recruitment rates, and timing of subjects' duration on study. The study will end 2 years from the last subject first dose or earlier if all patients are off study drug. Patients may be allowed to continue on study drug after the end of the study if the Investigator, in consultation with the sponsor's Medical Monitor, determines that continuing treatment will benefit the patient.

Figure 1 Study Schema

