6.2. Subject Completion Criteria

In Part 1, a subject will be considered to have completed the study if:

- they complete screening assessments, the 28-day DLT observation period, and taking a minimum of 75% of planned doses,
- they progress or die while receiving study treatment, or
- they are receiving ongoing study treatment at the time of the Sponsor's decision to close the study.

In Part 2, a subject will be considered to have completed the study if:

- they die while receiving study treatment,
- they progress while receiving study treatment and are followed until death, or
- they are receiving ongoing study treatment at the time of the Sponsor's decision to close the study.

Subjects who have not died, and are no longer being followed for survival are considered to have discontinued the study. The End of Study eCRF should only be completed when a subject is no longer being followed.

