6.3. Permanent Discontinuation from Study Treatment

Subjects will receive study treatment until disease progression, death or unacceptable toxicity, including meeting stopping criteria for liver chemistry defined in Section 4.7.1. The investigator may discuss with a GSK Medical Monitor continuing a subject who is receiving benefit but has met the criteria for disease progression, if the following criteria are met: Investigator-determined clinical benefit (e.g. symptomatic improvement), lack of

significant toxicity (no drug related non-hematologic grade 3/4 AEs within the last 4 weeks) and no therapeutic alternatives expected to provide durable responses.

In addition, study treatment may be permanently discontinued for any of the following reasons:

- Deviation(s) from the protocol
- Request of the subject or proxy (withdrawal of consent by subject or proxy)
- Investigator's discretion
- A clinically significant hematologic adverse event leading to an interruption of treatment for greater than 28 days. Subjects will be allowed up to a 28-day delay in dosing for hematologic toxicity to resolve or for scheduling difficulties. If the investigator and GSK Medical Monitor conclude that the benefit: risk supports continued treatment of a subject who has had a > 28 day treatment delay, then the subject may continue therapy with the approval of the GSK Medical Monitor.
- A clinically significant non-hematologic adverse event leading to an interruption of treatment for greater than 14 days. Subjects will be allowed up to a 14-day delay in dosing for non-hematologic toxicity to resolve or for scheduling difficulties. If the investigator and GSK Medical Monitor conclude that the benefit: risk supports continued treatment of a subject who has had a > 14 day treatment delay, then the subject may continue therapy with the approval of the GSK Medical Monitor.
- Persistent G4 thrombocytopenia for 4 weeks not attributed to disease or requires platelet transfusions for bleeding in the absence of the disease.
- Intercurrent illness that prevents further administration of study treatment(s)
- Subject is lost to follow-up
- Study is closed or terminated.

The primary reason study treatment was permanently discontinued must be documented in the subject's medical records and electronic case report form (eCRF).

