	SCR	First Treatment Phase (28 days)								Continuation Phase	EOT	SFU Q12W
		D 1	D4	D 8	D11	D 15	D18	D22	D25			
Vitamin B12, TSH, Free T4 or Free T3 ²⁰	X											
PK Blood samples		X ¹	X ⁸	X ⁸		X ²				Weekly x 4 wks (Wk 4-7), Wk 8 and every 4 wks ⁸		
Fetal hemoglobin (Hgb F)		X		X		X						
Pregnancy test ⁴	X									every 4 wks	X	
Blood samples for PD (peripheral blood) ^{3, 19}	X		X	X	bone marrow day ¹⁴					Wk 4, between Wk 6-8, Wk 12, then every 12 wks	X	
Blood samples for exploratory studies ^{3, 19} (peripheral blood)	X		X									
Bone marrow aspirate for PD ¹⁹	X					X ¹⁴				Wk 4, between Wk 6-8, Wk 12, then every 12 wks	X ⁵	
Bone marrow aspirate for exploratory studies ¹⁹	X ¹¹					X ¹⁴				Wk 4, between Wk 6-8, Wk 12, then every 12 wks	X ⁵	
Blood smear to measure blasts	X			X		X				Every week x 4 (Wk 4-7), Wk 8 then every 4 wks		
Bone marrow aspirate /biopsy for disease assessment ^{21, 22}	X ¹⁶					X ¹⁴				Wk 4, between Wk 6-8 ¹³ , Wk 12, then every 12 wks		
Telephone call for survival status ²³												X
PGX samples (buccal swab)	X											
PK blood sample on bone marrow day ¹⁵					X (on bone marrow day)					Wk 4, between Wk 6- 8, Wk 12, then every 12 wks.		
Transfusion Assessment ¹⁰	X			X		X		X		Every week x 4 (wk 4-7), Wk 8, then every 4 wks		
Adverse Events		Continuous										
Con Meds		Continuous										

1. A blood sample will be collected for PK analysis on D1 at pre-dose, 0.5, and 3 hrs post dose. . In the combination cohort, a blood sample for ATRA PK analysis will be collected at the same time points.
2. A blood sample will be collected for PK analysis on D15 at pre-dose, between 0.5 to 1 hour, and between 4 and 6 hours. In the combination cohort, a blood sample for ATRA PK analysis will be collected at the same time points.

3. Blood samples for PD, exploratory studies should be collected pre-dose.
4. For women of child bearing potential only. Serum pregnancy test is required for screening and EOT visits. Urine pregnancy test is adequate during study visits.
5. Bone marrow aspirate at the time of progression is optional for all subjects.
6. Height will be measured at screening only
7. These procedures do not need to be repeated on Day 1, if the screening visit was within 3 days and they were performed at screening.
8. PK blood sample should be taken pre-dose around the same time as CBC. PK sample will not be collected beyond 48 weeks.

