9. On clinic days, study drug should be taken in the clinic after safety procedures including CBC and PK/PD samplings, if applicable are completed.
10. Platelet and blood transfusions to be assessed at designated visits and summarized per unit on a weekly cumulative basis
11. A fresh bone marrow aspirate at baseline is required in Part 2
12. Twice weekly CBC monitoring may continue per institutional guidelines.
13. The assessment of response should occur between 1 – 4 weeks of count recovery (ANC > 1000/ μ l and platelets > 100,000/ μ l). Subjects should be off cytokine support (GCSF or GMCSF) for a minimum of 7 days before obtaining bone marrow to document remission.
14. Between D8 and D21, timing to be optimized based on emerging data.
15. PK blood sample should be collected prior to dosing on biopsy days. This sample should be collected if the bone marrow biopsy was performed on the non-planned visit days and the “PK blood sample” was not collected within the time frame
16. Baseline disease assessment should be completed within 21 days prior to dosing start. Cytogenetics testing should be performed as part of disease assessment at baseline. Cytomorphology is the preferred method to determine bone marrow blast counts. However, if a bone marrow aspirate cannot be obtained for cytomorphology review, a bone marrow biopsy is strongly recommended to determine the bone marrow blast count.
17. Sample should be collected at pre-dose on the day of bone marrow aspirate collection.
18. ATRA combination only
19. PD and/or exploratory sample (peripheral blood and BMA) collection may be stopped earlier at the sponsor’s discretion
20. Free T3 to be tested only when clinically indicated
21. At any time point in the study, if a bone marrow aspirate is found to be hemodilute (no spicules) or uninterpretable, then a bone marrow biopsy is strongly recommended to be collected at the next disease assessment time point in addition to the aspirate to ensure the conduct of a disease assessment.
22. BM slides may be evaluated for changes in morphology.
23. The Survival FU visit should be completed every 12 weeks after documented disease progression (or after initiation of another anticancer treatment). Subjects should be contacted every 12 weeks (\pm 2 weeks) until death occurs.

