13.8.1. Anti-Cancer Activity Analyses

For Part 1, anti-tumor activities will be evaluated based on clinical evidence and response criteria. If the data warrant, the response data will be summarized by dose level.

The primary aim of Part 2 is to detect a clinically meaningful response rate of 30% relative to a 10% response rate suggesting no activity.

Response rate (RR) is defined as the percentage of subjects who achieved CR, CRp, PR or morphologic leukemia-free state (MLFS) among subjects who received at least one dose of treatment. Response rate and the associated 2-sided 95% exact confidence limits will be provided. A waterfall plot of percent change from baseline in bone marrow blasts and peripheral blasts will be provided.

As a secondary analysis, if data warrant, PFS, OS, DOR, and TTR will be evaluated using the Kaplan-Meier method. Summaries of median time to event, quartiles and 95% CIs will be presented.

For the analysis of PFS, if the subject received subsequent anti-cancer therapy prior to the date of documented events, PFS will be censored at the last adequate assessment (e.g. assessment where visit level response is CR, CRp, PR, MLFS, or SD) prior to the

initiation of therapy. Otherwise, if the subject does not have a documented date of events, PFS will be censored at the date of the last adequate assessment. For the analysis of overall survival (OS), the last date of known contact will be used for those subjects who have not died at the time of analysis; such subjects will be considered censored. Further details on rules for censoring will be provided in the RAP. Sensitivity analyses of PFS and further details on censoring rules will be provided in the RAP. Progression free survival (PFS) and overall survival (OS) will be summarized using Kaplan-Meier method.

The duration of response is defined for the subject or subjects with a CR, CRp, MLFS, or PR, as the time from the first documented evidence of a CR, CRp, MLFS, or PR until the first documented disease progression or death due to any cause. Censoring rules for duration of response will be outlined in detail in the RAP.

Time to Response is defined, for subjects with a CR, CRp, MLFS, or PR, as the time from first dose to the first documented evidence of responses (PR or better).

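### Survival calls begin only after documented progression or new anticancer therapy, so a subject who stops treatment with neither has no scheduled contact after the EOT visit beyond adverse-event follow-up, and a later death may be missed for PFS and DoR

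*Protocol*

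**What the plan says.** **Trigger for survival contact.** Protocol Section 7.1, Table 4 footnote 23 (Part 2) and Table 3 footnote 26 (Part 1) carry the same rule: "The Survival FU visit should be completed every 12 weeks after documented disease progression (or after initiation of another anticancer treatment"). The next sentence reads "Subjects should be contacted every 12 weeks" and continues until death. The only entry in the survival follow-up column is "Telephone call for survival status".

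**Disease assessment.** The Part 2 row "Bone marrow aspirate /biopsy for disease assessment" runs from screening through weeks 4, 6–8 and 12, then every 12 weeks. Its EOT and survival follow-up cells are empty, as are those of the blast-smear row. Table 3 has the same pattern.

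**Stopping without progression.** Section 6.3: "Subjects will receive study treatment until disease progression, death or unacceptable toxicity". It also lists subject request, investigator discretion, prolonged interruption and persistent thrombocytopenia. After stopping it promises safety assessments only. Section 8.5 collects AEs and SAEs for 28 days and follows ongoing ones to resolution, stabilisation or loss to follow-up.

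**Endpoints and censoring.** Section 2 makes death from any cause a PFS event and death a DoR event. Under Section 13.8.1, for a subject without a documented event, "PFS will be censored at the date of the last adequate assessment". DoR censoring follows the PFS rules, and OS is censored at last known contact.

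**Completion and study end.** In Part 2 the Section 6.2 completion category that mentions follow-up to death is "they progress while receiving study treatment and are followed until death". Section 4.1: "The study will end 2 years from the last subject first dose or earlier if all patients are off study drug". Section 6.4 treats the study as complete once 80% of Part 2 subjects have withdrawn. Section 14.6 uses the last visit of the last subject.

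**The concern.** The calls reach the wrong subjects for PFS and DoR. Someone with documented progression has already had the event. Someone who starts another therapy is already censored for PFS under Section 13.8.1. The calls as triggered can therefore add no PFS event. The subjects in whom a later death would still count are those with neither trigger, and they are the ones without a scheduled call.

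If subjects who stop for toxicity then run a higher risk than those still on treatment, censoring them near the stop makes Kaplan-Meier PFS and DoR too long. Both are Part 2 secondary endpoints. In Part 1, footnote 26 has the same trigger, and the SAP lists deaths for all treated subjects (Listing 44), so late deaths after such a stop may be missing there too.

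Separately, a rule that contacts subjects until death does not sit with a study that may close as soon as everyone is off drug.

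**Working it through.** **1. The plan's own figures.** The only Part 2 operating characteristics stated are for the response rate (Section 13.4.2, maximum 30 subjects, 10% against 30%). An exact binomial recursion over the Figure 3 stopping boundaries, with success at 6 or more responses in 30, gives:

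| Quantity | Stated | Recomputed |
|---|---|---|
| Type I error | 0.064 | 0.0637 |
| Power | 0.89 | 0.8913 |
| Early stop if futile | 0.88 | 0.8816 |
| Early stop if effective | 0.084 | 0.0838 |

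Follow-up after stopping does not enter these figures. For PFS, DoR and OS the protocol states no event number, precision or dropout rate, so there is nothing to reproduce.

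**2. Contact after stopping, by type of subject** (Sections 7.1, 8.5 and 13.8.1).

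| Status at stop | Scheduled contact after EOT | PFS status |
|---|---|---|
| Progression documented | AE follow-up, then 12-weekly calls | Event already counted |
| No progression, starts new therapy | AE follow-up, then 12-weekly calls | Censored before the new therapy |
| No progression, no new therapy | AE follow-up only | Censored at last adequate assessment unless a death becomes known |

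The third row is the gap.

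**3. Size of the possible bias, as an illustration.** The documents give neither the share who stop without progression nor the hazard afterwards. Assumptions:
- constant event hazard on treatment h = ln 2 / 4 = 0.173 per month. The 4 months is the median survival for refractory AML in Section 1.4.2, used only to set a scale;
- share s stopping before an event, 20% or 40%, so stopping hazard c = h·s/(1 − s) = 0.043 or 0.116 per month;
- hazard k·h after the stop, k from 1 to 3;
- every such subject censored at the stop.

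True event-free probability:

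S(t) = exp[−(h + c)t] + c/(h + c − kh) · {exp(−kht) − exp[−(h + c)t]}

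Kaplan-Meier with censoring at the stop estimates exp(−ht), median 4.0 months. Solving S(t) = 0.5:

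| k | True median, s = 20% | Overstated | True median, s = 40% | Overstated |
|---|---|---|---|---|
| 1 | 4.00 | 0% | 4.00 | 0% |
| 1.5 | 3.86 | 4% | 3.68 | 9% |
| 2 | 3.76 | 6% | 3.47 | 15% |
| 3 | 3.62 | 10% | 3.20 | 25% |

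The last cell is 4.0/3.20 = 1.25. At 6 months the reported rate is 35.4%. In the worst cell the true rate is 24.3%, a gap of about 11 points. The percentages for the median depend only on s and k, because the 4-month scale cancels. Of 30 subjects, 20–40% is 6 to 12.

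**The case against.** Several points on the other side stand.

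- **EOT is not empty.** It falls within 14 days of the last dose and includes a complete physical examination and a CBC. Table 5 lists a blast count under hematology, and Appendix 6 allows progression on peripheral blasts alone. A reader might infer from the blank marrow cell that no visit could document progression at the stop. That is not so; the gap begins after EOT.
- **Some later deaths are captured.** AEs and SAEs run to 28 days and ongoing ones longer, and deaths from the disease go on the Death eCRF. It would be wrong to say that deaths after stopping are not collected at all.
- **Section 6.2 does place these subjects.** Its closing lines count those alive and no longer followed as having discontinued the study. That is a disposition label; it does not create follow-up.
- **The footnote's second sentence** has no trigger of its own and could be read as covering everyone. It also gives no separate starting point, so a site following the first sentence would not call these subjects. If universal contact was intended, the edit only says so.
- **Informative censoring is assumed.** At a post-stop hazard ratio of 1 there is no bias, and at 20% stopping the shift is at most about 0.4 months, small beside the uncertainty of a median from at most 30 subjects.
- **No planned report is affected through PFS, DoR or OS.** SAP Section 2.1 states that Part 2 was not initiated. The SAP's only efficacy table is best response and response rate.

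**Conclusion.** The point holds as a gap in the protocol's follow-up schedule. Subjects who stop with neither documented progression nor new therapy have no scheduled contact after EOT beyond adverse-event follow-up. Deaths that the PFS and DoR definitions count may therefore be missed.

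The size is conditional: 0–25% overstatement of the median under the stated assumptions, and nothing at equal hazards. A reader might conclude that PFS, DoR and OS are all shown to be too long. The documents do not support that. They give no stop rate and no post-stop hazard. For OS, new therapy does trigger the calls, and the direction is uncertain: losing sight of responders who stopped for toxicity could shorten the curve. OS appears in Section 13.8.1 but is not a listed endpoint in Section 2.

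What is affected is the protocol's secondary Part 2 endpoints and the completeness of late deaths in Part 1. The primary response rate and its design figures are not. The conflict between contact until death and the end-of-study rules needs no assumption about hazards.

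**What to change.** - **Footnotes 23 and 26.** Start 12-weekly telephone contact at the EOT visit for all subjects, whatever the reason for stopping, until death, withdrawal of consent or study end.
- **Content of the call.** Record death, progression or relapse documented in routine care, and new anticancer therapy, each with its date.
- **Section 13.8.1.** State that deaths found this way, and progression documented in routine care, count as PFS and DoR events if they precede new therapy. Without this sentence it is unclear how progression learned by telephone fits a rule built on adequate assessments.
- **End of study.** Reconcile Sections 4.1 (all subjects off drug), 6.4 (80% withdrawn) and 14.6 (last visit) with contact until death, so that one rule says when calls stop.

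Cost: wording changes, a few more calls, and slightly longer follow-up for some subjects. No marrow or clinic visit is added. Progression after EOT will still be dated from routine care, so those dates will be less exact than on-study assessments.

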7.2. Demographic/Medical History and Baseline Assessments

The following demographic parameters will be captured during Screening: year of birth, gender, race and ethnicity.

Medical/medication history assessed as related to the eligibility criteria listed in Section 3.2. Medical, surgical, and treatment history including date of first diagnosis, best response to prior systemic therapy, histology, and current sites of disease will be taken as part of the medical history and disease status.

Details concerning concomitant medication will be recorded starting from screening through post-study follow-up. At a minimum, the drug name, route of administration, dose and frequency of dosing, along with start and stop dates should be recorded.

Fasting will be required for screening clinical laboratory tests.

Baseline (Screening) assessments obtained will include:

- Complete physical examination, including height (in cm) and weight (in kg).
- Vital signs (blood pressure, temperature, respiratory rate, pulse rate)
- Eastern Cooperative Oncology Group (ECOG) performance status
- Clinical laboratory tests: hematology, clinical chemistry, coagulation parameters, vitamin B12, TSH, free T3 or free T4 (see Table 5 for full list of laboratory tests required at screening). Patients should have baseline thyroid function, vitamin B12, and metabolic panel within acceptable limits (FDA request May 2015).
- Lipid panel (ATRA combination only): triglyceride and cholesterol
- Serum beta-human chorionic gonadotropin (β -HCG) pregnancy test for female subjects of childbearing potential only
- 12-lead electrocardiogram (ECG)
- Echocardiogram (ECHO) or multi-gated acquisition (MUGA) scan
- Baseline disease assessment and bone marrow aspirates
- Review of concomitant medications
- Montreal Cognitive Assessment (MOCA)

Procedures conducted as part of the subject's routine clinical management (e.g., blood count, imaging study) and obtained prior to signing of informed consent may be utilized for Screening or baseline purposes provided the procedure meets the protocol-defined criteria and has been performed in the timeframe of the study.

